### 12 Trial Subjects

The subsections in this section include specifications for reporting subject disposition and treatment/trial discontinuations. Additionally, procedures for reporting protocol deviations are provided.

### **12.1 Disposition of Subjects and Discontinuations**

Subject disposition will be described in terms of the number and percentage of subjects in each of the following disposition categories:

- Total number of subjects screened (i.e. subjects who gave informed consent).
- Number of subjects who discontinued from the trial prior to randomisation / enrolment, overall and grouped by the main reason (e.g. did not meet eligibility criteria, withdraw of consent, progressive disease, etc.).
- Number of randomised / enrolled subjects, overall and grouped by infection severity (i.e. light, moderate/heavy), cohort as well as analysis set.
- Number of randomised / enrolled subjects who discontinued the trial after randomisation / enrolment, overall and grouped by cohort as well as main reason for discontinuation (e.g. adverse event, lost to follow-up, etc.).
- Number of randomised / enrolled subjects who completed the trial, overall and grouped by cohort. Only those subjects with *End of Study* visits, not due to early withdrawal, will be considered as subjects who completed the trial.

## 12.2 Protocol Deviations

## **12.1.1 Important Protocol Deviations**

The following summary tables and listings of important protocol deviations will be provided (separately for pre-/post enrolment deviations):

- Frequency table of deviations from each cohort, grouped by reason of important protocol deviations
- Listing of important protocol deviations

## 12.1.2 Reasons Leading to the Exclusion from an Analysis Set

For subjects excluded from the mITT and PP analysis sets, the reasons for exclusion will be summarized and listed;

- Frequency table of exclusion from each cohort, grouped by analysis set and reason for exclusion
- Listing of reasons of exclusion from analysis sets, grouped by analysis set and cohort

## **13 Demographics and Other Baseline Characteristics**

If not stated otherwise, summaries will be presented for the SAF analysis set.

## **13.1 Demographics and Baseline Physical Characteristics**

Demographic characteristics will be summarized using the following information from the Prescreening Visit (Day -28 to -1) CRF pages.

- Demographic characteristics
  - Gender: male, female
  - Race/Ethnic: Black or African American, Asian, Native Hawaiian or other Pacific Islander, American Indian or Alaska Native, White, other, not collected.
  - Age (months and years): summary statistics
  - Age categories:
    - 3 months  $\leq$  age < 13 months
    - 13 months  $\leq$  age < 24 months
    - 2 years  $\leq$  age < 4 years
    - 4 years  $\leq$  age  $\leq$  6 years
- Height in cm at Baseline: summary statistics
- Weight in kg at Baseline: summary statistics
  - Body-mass index (kg/m^2) at Baseline: summary statistics

Specifications for computation:

- Age [months and years]:
  - For those subjects aged two years and older Age [in years] will be calculated as follows: (date of given informed consent date of birth + 1) / 365.25
  - For those subjects less than two years old Age [in months] will be calculated as follows: (date of given informed consent date of birth + 1) / 30.4375
  - In case of missing day for at least one date, but month and year available for both dates: Missing day will default to the first day of the month, i.e. 01
  - In case of missing month for at least one date, but year available for both dates: Missing month will default to the first month of the year, i.e. January or 01

### 13.2 Medical History

The medical history will be summarized from the "Medical History" eCRF page, using the Medical Dictionary for Regulatory Activities (MedDRA), version 19.0, preferred term as event category and MedDRA system organ class (SOC) body term as Body System category.

Medical conditions will be summarized by SOC and preferred term, providing the number and percentage of subjects with the condition, as well as the number and percentage of conditions. Summaries will be presented two-fold, first ordered in terms of decreasing percentage for SOC, and PT within SOC, and second, ordered alphabetically for SOC, and PT within SOC.

## 14 Previous, Concomitant and Prohibited Medications/Procedures

**Previous medications** are medications, other than trial medications and pre-medications for trial drug, which are taken within four weeks prior to first IMP administration and if the end date of the medication < date of "study day 1".

Previous treatment will be summarized from the "Concomitant Medications" eCRF page. Anatomical Therapeutic Chemical (ATC) term 2nd level and preferred term will be tabulated as given from the WHO Drug Dictionary March 2016 version. In case multiple ATC's are assigned to a drug, all ATC-2nd level will be used for reporting.

**Concomitant treatments** are medications, other than trial medications, which are taken by subjects any time on-trial (the end date of the medication  $\geq$  date of "study day 1", or medication that is ongoing with a start date  $\geq$  date of "study day 1").

Concomitant treatment will be summarized from the "Concomitant Medications" eCRF. ATC-2nd level and preferred term will be tabulated as given from the WHO Drug Dictionary current version. In case multiple ATC's are assigned to a drug, all ATC-2nd level will be used for reporting.

**Prohibited medications** are medications, other than trial medications, listed in section 6.5.2 of the trial protocol that are taken by subjects at any time.

- Prohibited prior medications will be summarized from the "Prior Drug History" eCRF page. ATC level 2 and preferred term will be tabulated as given from the WHO Drug Dictionary version of March 2016. In case multiple ATC's are assigned to a drug, all ATC-2nd level will be used for reporting.
- Prohibited concomitant medications, which includes medications that were started prior to dosing but were not stopped prior to dosing, will be summarised and listed separately. Prohibited concomitant medications will be identified from the "Concomitant Medications" eCRF page, using Appendix B as guide. ATC level 2 and preferred term will be tabulated as given from the WHO Drug Dictionary version of March 2016. In case multiple ATC's are assigned to a drug, all ATC-2nd level will be used for reporting.

All **Concomitant Procedures**, which were undertaken any time on trial, will be summarized according to the eCRF page "Concomitant Procedure".

- Concurrent procedures will be listed by verbatim term.
- Number of subjects with concomitant procedures (Prior, on or after the first day of trial treatment or within 28 days after last dose of trial treatment) overall will be presented.

## **15** Treatment Compliance and Exposure

Compliance and exposure will be reported for the mITT and PP analysis sets.

All dosing calculations and summaries will be based on "Treatment (D1)" CRFs pages.

### **Compliance will be derived as follows:**

• 100 × {Actual number of doses administered / expected number of doses that were to be administered}, rounded to the nearest integer using the ROUND() function.

Compliance will be categorised as:

- $\circ \quad \text{Compliance} = 0\% \qquad \qquad \{0 \text{ doses administered in C1}; 0 \text{ doses in C2-C9}\}$
- $\circ$  Compliance = 33%
- $\circ$  Compliance = 67%
- {1 doses administered in C1}
- $\{2 \text{ doses administered in C1}\}$
- $\circ$  Compliance = 100% {3 doses administered in C1; 1 dose in C2-C9}

Compliance will be summarised by cohort and compliance level, as well as listed by cohort and subject.

### Exposure, in terms of dosing, will be derived as follows:

• Exposure:

{Cumulative Actual Dose [mg]}

If *Actual Dose* is missing, exposure will be derived as {Cumulative *Planned Dose* [mg]}, which will be flagged in listings

• Exposure with respect to weight:

{Cumulative Actual Dose [mg]} / weight [kg], as calculated using the weight measurement at dosing

If *Actual Dose* is missing, exposure will be derived as {Cumulative *Planned Dose* [mg/kg]}, which will be flagged in listings

Handling of other missing data:

• In case the start date is missing, it is assumed that the first dose of trial medication is given at the randomisation date. The randomisation date will replace incomplete dates of the first dose of trial medications.

## 16 Endpoint Evaluation

## 16.1 Primary Endpoint Analyses

## 16.1.1 Primary Analyses of Overall Clinical Cure Rate

No hypothesis testing will be performed. Point estimates and corresponding two-sided 95% CIs will be determined.

#### Analysis set(s):

• Primary analyses will be based on the mITT and PP analysis sets.

### **Overall clinical cure rate:**

Subjects cured of infection during the trial will be labelled as "responders". Responders will be defined as subjects with no parasite eggs (as determined by Kato-Katz method) in the End of Study

stool samples, 14-21 days after treatment, according to the eCRF page "Follow-up visit on D14-D21". Responders and non-responders will be coded as follows:

- For responders, *response* = 1
- For non-responders, response = 0

If the End of Study Kato-Katz egg count is missing, it will be imputed using the Last Observation Carried Forward (LOCF) approach. Subjects with missing data will be considered non-responders.

The proportion of responders in each cohort will be determined based on a binomial distribution. Exact 95% CIs will be calculated based on the Clopper-Pearson method. The PROC FREQ procedure in SAS will be used with the appropriate BINOMIAL and EXACT statements for point estimates and corresponding 95% CIs.

Point estimates and corresponding 95% CIs will be presented for cure rate, in terms of proportion of responders, by cohort. Response will be listed by cohort and subject. Estimates of cure rate will be presented graphically in the form of forest plots presenting means and 95% CIs.

Results will be presented for each analysis set.

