6.3 Assignment to Treatment Groups

Subjects will receive their subject identification number after one of the parents/legal representatives has signed the informed consent and children have given their assent, when applicable. Subjects who meet all inclusion criteria and none of the exclusion criteria will be randomized after recheck of eligibility on Day 1.

The Investigator or his/her designee will allocate a randomization number to each subject in each stratification group following a sequential order before first dosing of IMP (see also Section 8.2).

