8.2 Randomization

Part 1: Treatment allocation will be random and balanced at a ratio of 1:1:1:1:1.1. Randomization will be stratified by the infection severity (40% moderate/heavy and 60% light infections). After 20 subjects/arm are randomized, the SMC will decide on the inclusion of the 7^{th} arm.

Randomization will continue for arms C1-C6 at a ratio of 1:1:1:1:1:1 until a total of 40 subjects/arm are randomized.

If the C7 arm is included, randomization will continue with an allocation ratio of 1:1:1:1:1:3. If C7 arm is not included, the allocation ratio will remain the same (1:1:1:1:1).

Randomisation lists indicating a randomisation number and which treatment is to be given, will be produced prior to the start of the trial by the statistician at the PPD. Based on the randomisation lists sequentially numbered sealed envelopes which contain a randomisation number and the treatment allocation will be prepared. The sealed randomization envelopes will look identical and will be kept in a locked cupboard to which only the study pharmacist will have access.

Part 2: There is no randomization in this part.

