## 7 Sample Size/Randomisation

## 7.1 Sample Size

Part 1: this study is exploratory. There is no hypothesis testing.

The sample size is based on the minimum number of subjects to reach a meaningful precision of the primary efficacy endpoint estimate (cure rate) in each arm, considering the stratification factor.

There are limited historical data on the impact of the severity of infection on the observed cure rate. In the recent study by Keiser et al. (unpublished data), the observed cure rate in *S. mansoni* infected children varied between 55% and 60% in moderately infected children and 70% and 85% in light infected children depending on the dose. The table below presents the overall cure rate projections according to different assumptions of true cure rate in mild (low) and moderately infected children.

Overall cure rate (95%CI),	Assump	tions of Cure F	Rate in Light In	fections
(N=50)	70%	75%	80%	85%

	50%	62% (48%, 74%)	65% (52%, 78%)	68% (56%, 80%)	71% (60%, 82%)
Assumptions of	55%	64%	67%	70%	73%
Cure Rate in		(50%, 76%)	(54%, 80%)	(58%, 82%)	(62%, 84%)
Moderate/Heavy	60%	66%	69%	72%	75%
Infections		(52%, 78%)	(56%, 80%)	(60%, 84%)	(64%, 86%)
	65%	68% (54%, 80%)	71% (58%, 82%)	74% (62%, 86%)	77% (66%, 88%)

A minimum-clinical meaningful cure rate is considered as equal to 70%. With 50 evaluable patients enrolled, stratified as 40% moderate/heavy and 60% light, the corresponding 95% CI lower bound of an observed cure rate of 70% would be above ~58%, depending on potential difference between the strata. This sample size would also provide the minimum number of subjects to estimate the cure rate within strata.

Considering the efficacy criteria for the selection of the dose (observed cure rate >70%), through simulations, the table below presents the probability of observing an overall cure rate >= 70% based on different scenarios of true cure rates based on different strata, assuming a stratification of 40% moderate/heavy infections and 60% light infections.

Probability of observ	ring a	Assumptio	ns of Cure I	Rate in Ligh	t Infections
cure rate $\geq 70\%$ , N	=50,	70%	75%	80%	85%
	50%	15%	27%	45%	64%
Assumptions of Cure Rate in	55%	23%	38%	57%	76%
Moderate/Heavy Infections	60%	33%	51%	70%	85%
intections	65%	45%	63%	80%	92%

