## 7.2 Randomisation

Part 1: Treatment allocation will be random and balanced at a ratio of 1:1:1:1:1:1. Randomisation will be stratified by the infection severity (40% moderate/heavy and 60% light infections). After 20 subjects/arm are randomized, the SMC will decide on the inclusion of the 7th arm.

Randomisation will continue for arms C1-C6 at a ratio of 1:1:1:1:1:1 until 40 subjects/arm are randomized.

If the C7 arm is included, randomisation will continue with an allocation ratio of 1:1:1:1:1:1:3 until a total of 60 subjects/arm are randomized in the 7 arms. If C7 arm is not included, the allocation ratio will remain the same (1:1:1:1:1) until a total of 60 subjects/arm are randomized in the 6 arms, as shown below.

Randomisation lists indicating a randomisation number and which treatment is to be given, will be produced prior to the start of the trial by the statistician at the **PPD**...Based on the randomisation lists sequentially numbered sealed envelopes which contain a randomisation number and the treatment allocation will be prepared. The sealed randomisation envelopes will look identical and will be kept in a locked cupboard to which only the study

Part 2: There is no randomisation in this part.

pharmacist will have access.

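### The stated lower confidence bound of about 58% at an observed 70% cure rate is not what the planned Clopper-Pearson interval gives (55.4%), and the plan does not say whether the 40/60 severity mix behind the 70% criterion is enforced.

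*SAP*

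**What the plan says.** **Design.** Protocol 8.2 states: "Randomization will be stratified by the infection severity (40% moderate/heavy and 60% light infections". SAP 7.2 says the same. Under Protocol 6.3 the investigator or a designee "will allocate a randomization number to each subject in each stratification group following a sequential order".

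**Sample size.** SAP 7.1 sets the clinical threshold: "A minimum-clinical meaningful cure rate is considered as equal to 70" per cent. It introduces the probability table with "Considering the efficacy criteria for the selection of the dose (observed cure rate >70" per cent), and runs the simulations "assuming a stratification of 40% moderate/heavy infections and 60% light infections". Protocol Table 8 gives the same figures. On precision, SAP 7.1 says that with 50 evaluable patients "the corresponding 95% CI lower bound of an observed cure rate of 70% would be above ~58" per cent, with a qualifier that this depends on how far the strata differ.

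**Analysis.** SAP 16.1.1: "The proportion of responders in each cohort will be determined based on a binomial distribution". The interval is exact (Clopper-Pearson), and no stratum weights are given. Protocol 8.5.2 agrees. Severity enters in SAP 16.1.2, as supportive work: cure rates by cohort and severity, a logistic model with severity as a covariate, and dose-response curves by severity.

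**Timing of C7.** Under SAP 7.2, C1 to C6 each reach 40 children first. If C7 is opened, allocation continues at 1:1:1:1:1:1:3 until every arm has 60. All 60 C7 children therefore enter in the last phase, alongside only 20 of the 60 in each other arm.

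**The concern.** The sample-size section and the analysis section use different calculations. The first works with two strata in fixed proportions. The second pools all children in a cohort. This has two possible consequences.

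- **Precision.** A reader of SAP 7.1 expects an arm that just reaches 70% to carry a lower bound of about 58%. The interval that will be reported is wider.
- **Meaning of 70%.** SAP 7.1 cites cure rates of 55–60% in moderate and 70–85% in light infection. With a gap that large, a crude rate compared with a fixed 70% reflects the severity mix as well as the drug. At 40/60 this does no harm, since that is the mix the threshold was examined under. At another mix, the same drug has a different chance of reaching 70%. C7 could also differ in mix from C1–C6 because it enrols later. What is at stake is the reading of the efficacy evidence that goes to the Safety Monitoring Committee (SMC) for choosing the Part 2 dose.

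**Working it through.** **Inputs.** From SAP 7.1: N = 50, split as 30 light and 20 moderate/heavy; the cell with true cure 85% light and 60% moderate/heavy; the cell with 80% and 55%; the ≥70% rule used in the tables, which is X ≥ 35 cured of 50. From SAP 16.1.1: Clopper-Pearson 95%. Mixes other than 40/60 are assumptions, because the documents give none.

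**1. Reproducing the plan's probability.** X is the sum of Binomial(30, 0.85) and Binomial(20, 0.60). The true overall rate is 0.6 × 0.85 + 0.4 × 0.60 = 75%. Exact convolution gives P(X ≥ 35) = 84.7%, against about 85% stated. All 16 cells of the table reproduce to within 0.8 points. (The text above the table writes >70%; with X ≥ 36 this cell would be 75.6%, so the table uses ≥70%.)

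**2. Where the 58% comes from.** For 80% light and 55% moderate/heavy the overall rate is 0.6 × 0.80 + 0.4 × 0.55 = 70%. The 2.5th and 97.5th percentiles of Binomial(30, 0.80) + Binomial(20, 0.55), divided by 50, are 58% and 82%. These are the limits printed in that cell of the SAP table. They describe the spread of the estimate under an assumed truth. They are not the interval that will be computed from data.

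**3. What the planned interval gives.** The Clopper-Pearson lower limit is the 0.025 quantile of Beta(x, n−x+1), and the upper limit is the 0.975 quantile of Beta(x+1, n−x).

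- 35/50 = 70%: 55.4% to 82.1%.
- 42/60 = 70%, if all 60 randomised children are in the denominator: 56.8% to 81.2%.

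Neither lower limit reaches 58%.

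**4. How much of the gap is due to strata.** At an observed 70%, made up of 80% and 55%:

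- Stratified normal approximation: SE = √(0.36 × 0.80 × 0.20/30 + 0.16 × 0.55 × 0.45/20) = 0.0624; lower limit 0.70 − 1.96 × 0.0624 = 57.8%.
- Pooled normal approximation: SE = √(0.70 × 0.30/50) = 0.0648; lower limit 57.3%.
- Pooled exact: 55.4%.

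Of the 2.4 points between 57.8% and 55.4%, about 0.5 come from the strata and 1.9 from exact versus approximate method.

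**5. Effect of case mix on the crude rate.** True rates are held at 85% light and 60% moderate/heavy, N = 50. The last column uses the standardised rate, 0.6 × light + 0.4 × moderate/heavy.

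| Light / moderate-heavy | True crude rate | P(crude ≥70%) | P(standardised ≥70%) |
|---|---|---|---|
| 40 / 10 | 80.0% | 97.3% | 76.7% |
| 35 / 15 | 77.5% | 92.9% | 80.0% |
| 30 / 20 (planned) | 75.0% | 84.7% | 84.7% |
| 25 / 25 | 72.5% | 72.3% | 80.7% |
| 20 / 30 | 70.0% | 57.0% | 80.5% |

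Each 10-point shift in mix moves the crude rate by 0.10 × (85 − 60) = 2.5 points. The standardised true rate stays at 75%.

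**6. C7, assumed illustration.** Take 40% moderate/heavy before C7 opens and 60% after. Each of C1–C6 has 40 × 0.4 + 20 × 0.6 = 28 of 60 moderate/heavy; C7 has 60 × 0.6 = 36 of 60. With identical stratum cure rates (85% and 60%), the expected crude rates are (32 × 0.85 + 28 × 0.60)/60 = 73.3% and (24 × 0.85 + 36 × 0.60)/60 = 70.0%. P(at least 42 of 60) is 78% and 56%.

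**The case against.** **The 40/60 may be a quota.** Stratified randomisation alone needs no percentages. The sentences in Protocol 8.2 and SAP 7.2, with lists and envelopes prepared before the start, can fairly be read as fixing stratum sizes. The crude rate then equals the 0.4/0.6-weighted rate and the case-mix argument disappears, for C7 as well. Dropout would not disturb this, because children with missing data stay in the mITT set as non-responders; removing malaria-treated children, or per-protocol exclusions, still could. This objection stands to the extent that the documents support either reading. A reader might infer that nothing holds the mix at 40/60; the documents do not show that.

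**The pooled interval is sound.** A reader might infer that it is invalid because it ignores the strata. It is not: at the planned mix with 85%/60% its coverage is 97.4%. Stratifying adds little precision (step 4).

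**Severity is not ignored.** SAP 16.1.2 plans severity-specific rates and a severity-adjusted model, and anyone could weight the stratum rates by hand. That is correct, but those outputs are supportive, and none is a cure rate on the 40/60 scale set against 70%.

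**The 58% is hedged, and 70% is not a mechanical gate.** The bound is given as approximate and dependent on the strata, and no stated criterion uses it. The trial is exploratory, and the SMC weighs safety with efficacy (Protocol 8.6, SAP 8.2). Both points limit the consequence. Neither makes 58% the planned interval's bound.

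**Conclusion.** Two findings stand.

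**The precision statement is wrong for the planned method.** At 35/50 the lower bound is 55.4%, not above about 58%. This needs no assumption about recruitment. It is an error in the planning text; it does not affect the validity of the analysis.

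**The status of 40/60 is unstated, and the primary rate depends on it.** If it is a quota, there is no problem beyond wording. If it is only an expected mix, the crude rate can move with case mix, and C7 could differ in mix from the other arms. The size (97%, 85% or 57% for the same drug) rests on true rates of 85% and 60%, one cell of the SAP's own grid, and on assumed shares of 20% and 60% moderate/heavy. Stratified randomisation should keep concurrent arms similar, so the comparison with 70% is more exposed than the ranking of C1–C6.

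It is tempting to conclude that the standardised rate should replace the crude rate for the 70% criterion. The documents do not support going that far: the mix may be fixed by design, and at the planned mix the two rates are the same number.

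**What to change.** 1. **SAP 7.1:** change the lower bound at an observed 70% from about 58% to about 55% for the Clopper-Pearson interval on 35/50, and label the intervals in the projection table as simulation percentiles.
2. **Protocol 8.2 and SAP 7.2:** state whether 40/60 is an enforced quota, per arm and including C7, and what happens if a stratum fills or falls short.
3. **SAP 16.1.1:** beside the pooled Clopper-Pearson result, add a cure rate standardised as 0.4 × moderate/heavy + 0.6 × light with a stratified 95% interval whose method is named in advance. Report it against 70% as a sensitivity analysis, with the observed severity mix of each arm.

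The cost is SAP wording, one clarifying sentence in the protocol, and one extra estimate per arm. Severity is already recorded at pre-screening (SAP 10.2.1), so no new data are needed. When the mix is off plan, the standardised rate is somewhat less precise because a smaller stratum carries a fixed weight. It corrects for the two severity strata only, not for other changes over time that might affect C7.
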